9.9 Safety Follow-up Period

The Safety Follow-Up visit will be within 30 days after the last dose of enzalutamide or prior to initiation of cytotoxic or investigational therapy, whichever occurs first. See **Schedule of Events**, above.

9.10 Off Study and End of Study

A subject is considered *off study* when he has completed the Safety Follow-Up visit. All subjects discontinuing study drug for any reason will have a Safety Follow-Up visit approximately 30 days after their last dose of study drug or prior to initiation of cytotoxic or investigational therapy, whichever occurs first.

Reasonable effort should be made to contact any subject lost to follow-up during the course of the study in order to complete study-related assessments and retrieve any outstanding data and study drug. Following unsuccessful telephone contact, an effort to contact the subject by mail using a method that provides proof of receipt should be attempted. Such efforts should be documented in the source documents.

The *end of the study* will occur when the last subject enrolled has completed his Safety Follow-Up visit. A database lock will occur once the data has been cleaned to the specifications in the data quality plan. The database will then be frozen, and no further changes will be permitted.

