6.1.3 Concomitant Medications

All concomitant medications must be recorded on the appropriate CRF. Concomitant medications will be assessed at Screening and all clinic visits. The dosage and regimen of the following medications and any chronic permitted concomitant medications should be stable during the screening period (≥ 4 weeks prior to randomization) and held constant throughout the study:

- Bisphosphonates (if applicable)
- Denosumab (if applicable)
- GnRH analogue.

Subjects must be receiving androgen deprivation therapy (continuing therapy with a GnRH analogue) during the treatment phase starting at visit 3, day 29. If androgen deprivation therapy is discontinued, the subject must permanently discontinue study treatment.

Subjects are encouraged to receive standard of care supplementation such as calcium and vitamin D.

Certain concomitant medications and therapies are excluded during study treatment. For subjects who experience disease progression and are eligible to continue to receive study treatment, certain other medications and therapies are excluded. These excluded concomitant medications and therapies during study treatment are:

- Corticosteroids for prostate cancer^a
- Cytotoxic chemotherapy
- Investigational agents
- Hormonal agents^b
- Biologics^c

a. Use for acute onset (or exacerbation) of illness not related to prostate cancer is allowed.

b. Luteinizing hormone-releasing and GnRH analogues are allowed.

c. Bone targeting agents (i.e. bisphosphonates or denosumab) are allowed if used to increase bone mass in men at high risk of fracture, in the opinion of the treating physician.

The risk of seizure may be increased in subjects with a history of seizures or other predisposing factors. The risk of seizure may also be increased in subjects receiving concomitant medications that may lower the seizure threshold.

Deviation from these guidelines should occur only if absolutely necessary for the well-being of the subject. Any deviation from the medication/treatment guidelines are to be recorded on the concomitant medication CRF. Additionally, the Duke principal investigator is to be notified to determine the subject's continued eligibility in the study.

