9.6 Treatment Period 1: ENZ-ADT plus either Usual Care or Exercise Training

Arm A, ENZ – ADT plus Usual Care: Beginning on Day 29 (week 5), subjects will be treated with androgen deprivation therapy (ADT) per standard of care (orchiectomy, GnRH agonist, or GnRH antagonist to maintain total testosterone <50 ng/dl for the remaining 32 weeks of the study). In addition, subjects will take enzalutamide (ENZ) 160 mg by mouth daily for the remaining 32 weeks of the study. The dosing of both the GnRH agonist and enzalutamide (160 mg daily) is the standard-of-care dosing. The treatment duration of approximately 8 months was selected to achieve maximal efficacy while minimizing toxicity and is based on intermittent hormonal therapy regimens studied in Phase III clinical trials.^{22,23} Concomitant medication will be evaluated at every clinic visit during enzalutamide therapy. Concomitant medications include all vitamins, herbal remedies, over the counter, and prescription medications.

Arm B, ENZ – ADT plus Exercise Training: Beginning on Day 29 (week 5), Subjects randomly allocated to this group will receive the same ADT-ENZ regimen as described above. In addition, subjects will continue the defined exercise training initiated during the Lead-In Period for a total of 16 weeks (through Day 113, week 17).

The window is ± 7 days for this period, EXCEPT Day 29 (week 5) which has a window of ± 3 days. See **Schedule of Events**, above.

Subject data to be collected during Treatment Period 1 includes:

- Physical Exam
- Height, Weight, BMI
- Vital Signs
- Performance Status (ECOG)
- Concomitant Medications
- Adverse Events
- CBC with Platelets (hemoglobin, hematocrit, platelet count, white blood cell count, total [absolute] neutrophils)
- Serum Chemistry (sodium, potassium, chloride, total CO₂ [bicarbonate], calcium, BUN, creatinine, glucose, albumin, total bilirubin, total protein, alkaline phosphatase, AST, ALT)
- Testosterone (Day 57 and 113)
- PSA
- CPET (Day 29 and Day 113)
- Chair Stand (Day 113)
- Timed Up and Go (Day 113)
- 6 Minute Walk Distance (Day 113; **Duke patients only**)
- Muscular Strength (*at least 24 hours before or after CPET on Week 4, Week 10 (not in conjunction with CPET) and week 17 in treatment period 2*)
- Muscle CSA (MRI; Day 113; **protocol v1-v15 only**)
- Muscular Endurance (*must be at least 24 hours before or after CPET to allow for adequate recovery on week 4, week 10 (not in conjunction with CPET) and week 17 in treatment period 2*)

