9.8 End of Treatment and Safety Follow-Up

The End of Treatment/Safety Follow-Up visit will be on Day 252 (-7/+30 days). See Section **9.7** and the **Schedule of Events**, above.

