9.11.2 Follow-up Requirements for Early Withdrawal

The Premature Withdrawal visit will be the same as the Safety Follow-Up visit. As mentioned above, all subjects discontinuing study drug for any reason will have a Safety Follow-Up visit approximately 30 days after their last dose of study drug or prior to initiation of cytotoxic or investigational therapy, whichever occurs first.

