12.4.3 Handling of missing values, censoring, and discontinuations

The primary analysis from baseline to week 17 will include only complete cases.

Patients without VO_2peak measured at week 17 who have one or more measurements during the period from week 17 to the end of week 36 will have their week 17 measurement estimated by interpolation from the end of week 4 to the closest measurement following week 17. A sensitivity analysis will be done including these patients with complete cases.

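### Men who stop study drug more than about 30 days before Day 113 go off study before the endpoint tests, and the complete-case primary analysis then omits them

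*Combined protocol and SAP*

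**What the plan says.** - **Exit rule.** Section 9.10: "All subjects discontinuing study drug for any reason will have a Safety Follow-Up visit approximately 30 days after their last dose of study drug", or sooner if cytotoxic or investigational therapy is about to begin. The same section counts a man as off study "when he has completed the Safety Follow-Up visit".
- **Timing elsewhere.** Section 9.9 words it differently: "The Safety Follow-Up visit will be within 30 days after the last dose of enzalutamide". Section 9.8 places the combined End of Treatment and Safety Follow-Up visit at Day 252 and points to 9.7 for its content.
- **Early withdrawal.** Section 9.11.2: "The Premature Withdrawal visit will be the same as the Safety Follow-Up visit".
- **A linked trigger.** Section 6.1.3: "If androgen deprivation therapy is discontinued, the subject must permanently discontinue study treatment".
- **Content of the exit visit.** The 9.7 list and the Day 252 column of the Schedule of Events have examination, laboratory tests, PSA and questionnaires. They have no CPET, chair stand, timed up and go, 6-minute walk, strength or DEXA.
- **Where the endpoint tests sit.** After baseline, 9.6 and the Schedule place CPET on Day 29 and Day 113 only. Chair stand, timed up and go, walk distance (Duke only) and DEXA are repeated on Day 113 only.
- **Analysis.** Section 12.1 makes the modified ITT set (baseline and week 17 both present) the primary population. Section 12.4.3: "The primary analysis from baseline to week 17 will include only complete cases".

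**The concern.** The exit rule ties the collection of a week-17 outcome to staying on drug. Whether a man is still on drug is settled after randomisation. It may be related to the outcome: the protocol makes fatigue and generalised muscle weakness adverse events of special interest (10.1.1), and it expects training to buffer the effect of hormonal therapy (9.5). If men who stop fare differently from men who continue, and the arms lose different numbers, the comparison of completers is no longer the randomised comparison.

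Some of this loss is avoidable. A man who stops in the early weeks of drug may be willing and fit to do a CPET on Day 113, yet the plan as written makes him off study before then. A CPET that was not done cannot be recovered at analysis, and with 20 men per arm a few missing values matter.

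**Working it through.** **1. Who is affected.** Inputs: drug start Day 29 (9.5, 9.6); CPET Day 113 with a window of ±7 days (Schedule of Events); exit visit about 30 days after last dose (9.10).

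- Window opens: 113 − 7 = Day 106. Off study before it opens if the last dose is before 106 − 30 = Day 76, which is 76 − 29 = 47 days after drug start.
- Nominal day: 113 − 30 = Day 83, or 83 − 29 = 54 days after drug start.
- Window closes: 113 + 7 = Day 120; 120 − 30 = Day 90.
- Time from drug start to Day 113: 113 − 29 = 84 days.

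So stops in roughly the first 47 to 54 of 84 days are affected. A man stopping later than about Day 83 can be tested before his exit visit, and stops after Day 113 do not touch the endpoint. Under the wording of 9.9 the exit visit may come sooner than 30 days, which would widen the affected group.

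**2. What the sensitivity analyses can use for him.**

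- *Interpolation (12.4.3)* needs a VO2peak between week 17 and the end of week 36. No CPET is scheduled after Day 113, and he is off study by then. It cannot include him.
- *LOCF (Section 5, 12.5)* does include him, but with his Day 29 CPET, taken at about the start of drug, or else his baseline value. For the functional tests only baseline exists, so his change is set to zero. In each case the carried value contains essentially no drug effect.

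**3. Power.** Inputs from 12.6: effect size 0.68, one-sided level 0.10, 20 evaluable per arm, stated power 80%. Noncentral t with df = 2n − 2 and noncentrality 0.68 × √(n/2).

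Reproduction: n = 20 gives 0.68 × √10 = 2.15 on 38 df, power 80.1%. The stated figure is confirmed. Section 6.1 enrols 40 and 12.6 needs 40 evaluable, so there is no allowance for loss.

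| Share without Day 113 CPET, each arm | n per arm | Power |
|---|---|---|
| 0% | 20 | 80.1% |
| 5% | 19 | 78.5% |
| 10% | 18 | 76.8% |
| 15% | 17 | 75.0% |
| 20% | 16 | 73.1% |
| 25% | 15 | 71.0% |

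The 15% row uses the loss rate from the 56-man calculation in 12.6; the other rates are assumptions. At 15%, three men per arm are missing. Recovering one of the three would bring power to 76.8%, two to 78.5%. Keeping 20 evaluable per arm through over-enrolment at 15% would need 20/0.85 = 23.5, so 24 per arm.

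**4. Bias (illustration only).** Let men who stop have a VO2peak change k SD worse than men who continue, with the same k in both arms, and let q be the share lost. Within an arm, completers' mean = full mean + k × q. The completers' B − A difference is therefore off by k × (q_B − q_A).

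- Equal loss, for example 15% and 15%: k × 0 = 0.
- Loss of 5% in one arm and 25% in the other (1 versus 5 men of 20), k = 0.5 to 1: 0.10 to 0.20 SD, or 0.10/0.68 = 15% to 0.20/0.68 = 29% of the design effect. Benefit is understated if usual care loses more and overstated if the exercise arm loses more.

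Both k and the unequal loss are assumed; the documents supply neither.

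**The case against.** **No rule cancels the Day 113 tests.** This is correct. Section 9.10 defines when a man is off study; it does not prohibit testing. Section 12.3 also tabulates men who discontinue treatment separately from men who do not complete follow-up, which suggests that the authors did not equate the two. But that section only describes reporting, and the contact effort in 9.10 is for men lost to follow-up, not for men known to have stopped drug. Neither keeps a man who has stopped on the schedule. What stands is that the loss follows from the off-study definition and the visit content, and a site could read the text otherwise.

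**Few men may be affected.** This also stands. Footnote j of the Schedule says that a PSA rise should not lead to stopping drug in the first 12 weeks, and 6.1.1 allows interruption and restart after toxicity. Some early losses will be refusals or men unfit for CPET, whom no rewording recovers. The number recoverable could be 0 or 1 per arm.

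**Testing a man off drug answers another question.** The objective concerns men receiving ENZ-ADT. A man who stops on Day 57 (week 9) would be tested 113 − 57 = 56 days later, with an enzalutamide half-life of 5.8 days (4.2.2). His value partly reflects time off drug. That is a fair point about interpretation, but collecting the value leaves both analyses possible; not collecting it settles the matter by default.

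**A stronger reading to avoid.** A reader might put the whole 15% in one arm with a 3 mL/kg/min deficit and infer a shift of 0.15 × 3 = 0.45 mL/kg/min. The documents do not support this: the 15% is overall loss to follow-up, not early drug stops, it was applied to both groups, and the deficit is assumed. Nor does any text put a man off study for stopping exercise training.

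**Conclusion.** The concern holds in limited form. Followed as written, the plan takes a man off study before the Day 113 tests if his last dose falls before about Day 83 (Day 76 for the start of the window), and the primary analysis then omits him. LOCF restores him only with a value from about drug start or earlier; interpolation cannot use him.

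The size is not known. No early drug-stop rate is given, so bias could be nil or could run in either direction, depending on how the arms differ. The power cost is bounded more easily: 75.0% instead of 80.1% if 15% of each arm had no Day 113 CPET, with only part of that due to this rule. A reader might infer that every man who stops drug is lost, or that the primary result is known to be biased; the text supports neither. This is a low-cost improvement to a small trial, worth making because the missing measurements cannot be obtained later.

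**What to change.** In 9.10 and 9.11.2, separate stopping study drug or ADT from leaving the study:

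- A man who stops drug has the Safety Follow-Up visit for safety but stays on study. He keeps the already scheduled Day 113 CPET, functional, strength and DEXA tests and the Day 252 questionnaires, unless he withdraws consent or the investigator considers testing unsafe.
- Define off study by completion of the Day 252 assessments or withdrawal of consent, not by the Safety Follow-Up visit after a drug stop.
- In 12.4, include his Day 113 value in his randomised arm. If an on-treatment answer is wanted, report it as a sensitivity analysis.
- Use one wording for the timing of the Safety Follow-Up visit in 9.8, 9.9 and 9.10.

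The cost is a wording amendment; the tests are already on the schedule for every randomised man. The downside is that some men return for testing after stopping drug, and their values reflect time off drug. No change to dosing or to the rules for stopping treatment is proposed.

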9.11 Early Withdrawal of Subject(s)

9.11.1 Criteria for Early Withdrawal

Subjects may voluntarily withdraw from the study at any time. The PI may also withdraw a subject from the study at any time based on his/her discretion. Reasons for PI-initiated withdrawal may include, but is not limited to the following:

- Adverse events
- Abnormal laboratory values
- Abnormal test procedure results
- Protocol deviation
- Administrative issues
- Disease progression, defined as follows:
 - o PSA progression. PSA is evaluated per the Schedule of Events in Section 9. If a measured PSA is higher than the preceding value, then the rising PSA will be confirmed in 4 weeks (\pm 1 week) in the same laboratory as the first two values. If that third PSA value is higher still and the range of values is 50% above the baseline, then the patient is off study treatment. If not, the patient will remain on study, and the PSA will once again be checked when the patient presents for his regularly scheduled clinic visit.
 - o Radiographic progression (in the opinion of the investigator)

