6.1.4 Randomization

Once the subject has been registered, completed screening, and found to eligible post-baseline testing, the study coordinator at Duke will request the subject's random assignment to one of the two treatment arms from the Medidata RAVE database.

For this pilot study, subjects will be randomly assigned with equal probability to either usual care or exercise training. A stratified block design will be used with randomization stratified by site only. Specifically, stratification will be: Duke versus MSKCC. This study is open label, meaning that neither subjects nor study personnel will be blinded to treatment assignment.

The site will then be notified by the RAVE database to which arm the subject has been assigned. For subjects who are not eligible and fail the screening process, no further action is necessary and no additional information will be collected. However, the number of screen failures and reason for screen failure will be collected at each site and tallied at the end of the study.

Case report forms will only be completed for those registered and randomized subjects, including those who do not receive treatment. However, subjects who do not receive the assigned treatment will be replaced and not counted toward the overall study sample size. Data limited to demographics will be collected for screen failures.

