9.5 Lead-In Period

Subjects will be randomized to usual care or exercise training up to 14 days prior to Day 1, but only after eligibility is confirmed and baseline exercise testing (specifically, CPET) has been performed. See **Sections 6.1.4** and **9.4** for randomization details. See also **Schedule of Events**, above.

Arm A, ENZ – ADT plus Usual Care: Subjects randomized to usual care will be asked not to make any changes in their physical activity beginning on Day 1. These subjects will start ENZ – ADT on Day 29 (week 5) after the 4 week lead-in period. This delay is felt to be insignificant from a clinical perspective. While two Phase III studies are currently examining this question (NCT00439751; NCT00110162), the delay in initiation of ADT in these studies is much longer than 4 weeks. There is currently no evidence that a delay, especially one as short as 4 weeks, in starting ADT in men with non-metastatic prostate cancer, affects outcomes.⁸⁸

Arm B, ENZ – ADT plus Exercise Training: Subjects randomized to exercise training will begin the exercise training program detailed below beginning on Day 1. The goal for the ENZ-ADT plus exercise training will be 3 supervised exercise sessions per week at an intensity between 50 and 100% of the individually determined exercise capacity (at baseline) for aerobic training and an intensity between 60% and 80% of one-repetition maximum (1-RM) for resistance training for 30-90 minutes/session. The exercise training intervention is designed such that participants begin exercising at a low intensity (~50%-60% VO₂peak) that is subsequently increased to more moderate to vigorous intensity (~70%-80% VO₂peak) when appropriate. All interventions will be individually tailored to each subject following the principles of aerobic or resistance training prescription guidelines for adults as recommended by the American College of Sports Medicine (ACSM).⁸⁹ All exercise sessions will also be performed in a supervised setting with one-on-one supervision by certified exercise physiologists, physical therapists, exercise physiology students under the supervision of an ACSM-certified exercise physiologist, or trained designee. The exercise prescription for each subject will be created centrally by either [name] group at MSKCC or the CPX Lab at Duke based on both the interpretation of the CPET plus Muscular Strength/1-RM data and a standardized template, within 24-48 hours of these tests.

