12.1 Analysis Sets

The intent-to-treat (ITT) population will consist of all randomized patients. The modified intent-to-treat (ITT) population will consist of all randomized patients who have both a baseline and week 17 evaluation. In the ITT analyses and the modified ITT analyses patients will be analyzed according to the study arm to which they were randomized. The modified ITT population will be the primary analysis population.

The per-protocol population will consist of all randomized patients with both baseline and week 17 measurements for the primary endpoint and prior to any analysis: have been deemed compliant and properly evaluated for efficacy per investigator, satisfied all inclusion and exclusion criteria, and correctly assigned treatment.

The safety population will be all patients with at least one safety evaluation.

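### Withdrawal by the unblinded PI under 9.11.1 ends follow-up without a week 17 CPET, so discretionary removals drop out of the primary analysis

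*Combined protocol and SAP*

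**What the plan says.** Section 9.11.1 gives the PI a general power: "The PI may also withdraw a subject from the study at any time based on his/her discretion". It adds: "Reasons for PI-initiated withdrawal may include, but is not limited to the following". The list that follows mixes safety grounds with protocol deviation and administrative issues. On blinding, 6.1.4 says that "neither subjects nor study personnel will be blinded to treatment assignment".

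Section 9.11.2 settles what is measured afterwards: "The Premature Withdrawal visit will be the same as the Safety Follow-Up visit". In the Schedule of Events, CPET appears at baseline, Day 29 and Day 113 only; the assessments listed in 9.7 for the period ending in the safety visit contain none.

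Section 12.1 defines two sets. "The intent-to-treat (ITT) population will consist of all randomized patients", and "The modified intent-to-treat (ITT) population will consist of all randomized patients who have both a baseline and week 17 evaluation". It then says: "The modified ITT population will be the primary analysis population". Sections 12.4.2 and 12.4.3 restrict the primary t-test to complete cases.

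The training target in 9.5, for Arm B only, is "3 supervised exercise sessions per week", worded as a goal. Arm A men are asked to leave their physical activity unchanged.

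**The concern.** Read together, these sections let someone who knows the allocation decide, after randomisation and without a safety reason, that a man leaves the study. If that happens before Day 113, his primary outcome is never measured and he is not in the primary comparison. Section 12.1 says that men are analysed in the arm to which they were randomised, but that protects only men who still have a week 17 value.

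The opportunity is not symmetric. Attendance exists only in Arm B, where the target amounts to 3 x 16 = 48 sessions, and 12.5 refers to weekly attendance logs, so poor attenders are identifiable well before week 17. If poor attenders gain less fitness, withdrawing them raises the Arm B mean change. No stopping of study drug is needed, and the clause can act in the four-week lead-in before any drug is given. A rule that kept only drug-stoppers in follow-up would therefore leave this route open.

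**Working it through.** **1. Does a withdrawn man really leave the primary analysis?**
- Measurement: the withdrawal visit is the safety visit (9.11.2), and no CPET is scheduled there (Schedule of Events, 9.7).
- Retrieval: 9.10 asks for efforts to complete assessments in men lost to follow-up. It does not mention men whom the PI withdraws.
- Primary set: baseline and week 17 values are both required (12.1, 12.4.2, 12.4.3).
- Interpolation (12.4.3): it needs a VO2peak after week 17, and none is scheduled.
- LOCF (12.5): it can bring the man back, but only in a sensitivity analysis.

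So he does leave it. Section 6.4 conflicts with this, since it calls a man evaluable on a baseline measurement alone.

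**2. The plan's own figure.** Section 12.6 (revised): 20 evaluable per arm, one-sided alpha 0.10, effect size 0.68, 80% power. The noncentral t gives 80.1% and the normal approximation 80.8%, so the figure reproduces. If losses were unrelated to outcome, losing 2 or 3 Arm B men would lower power to 78.4% or 77.5% with no bias. The issue is selection, not numbers.

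**3. Shift in the Arm B mean.** Inputs: 20 men per arm and an Arm B mean change of +1.0 (12.6). Assumed, because the documents give neither: k men withdrawn, each of whom would have changed by m. The range for m runs from 0 to -2.0, the latter being 12.6's usual-care assumption. k = 3 is 15% of 20, the loss rate in the initial calculation.

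Remaining mean = (20 x 1.0 - k x m) / (20 - k)

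| k | m | Remaining mean | Shift |
|---|---|---|---|
| 2 | 0 | 20/18 = 1.11 | +0.11 |
| 3 | 0 | 20/17 = 1.18 | +0.18 |
| 2 | -2.0 | 24/18 = 1.33 | +0.33 |
| 3 | -2.0 | 26/17 = 1.53 | +0.53 |

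Against the 3.0 difference of the superseded calculation this is 0.11/3.0 = 4% to 0.53/3.0 = 18%. The current design states only 0.68 SD. If the SD of 3.5 still applies, that is 0.68 x 3.5 = 2.38, and the range is 0.11/2.38 = 5% to 0.53/2.38 = 22%.

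**4. What LOCF would recover.** A man withdrawn in the lead-in carries his baseline value, so his change is set to 0. With m = -2.0 the Arm B mean becomes 24/20 = 1.20 (k = 2) or 26/20 = 1.30 (k = 3), leaving +0.20 or +0.30. A man withdrawn after Day 29 carries a value taken after training alone, before the ENZ-ADT effect under study.

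**5. Effect on the one-sided error.** Simulation, 100,000 trials per setting: no true effect, 20 per arm, the k poorest attenders removed from Arm B, pooled t-test at 0.10. The correlation between attendance and change is assumed; shifts use SD 3.5.

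| Correlation | Error, k = 2 | Error, k = 3 | Shift, k = 3 |
|---|---|---|---|
| 0 | 0.10 | 0.10 | about 0 |
| 0.3 | 0.13 | 0.15 | 0.27 |
| 0.5 | 0.16 | 0.19 | 0.45 |
| 1.0 (limit) | 0.25 | 0.34 | 0.91 |

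**The case against.** The strongest reply is that the plan treats non-attendance as data, not as a reason for removal. Nothing makes a missed session a protocol deviation, and three sessions a week is only a goal. Section 12.3 summarises sessions attended, 12.5 defines adherence and attrition as outcomes, and 12.1 has a separate per-protocol set for excluding non-compliant men. That structure suggests the authors expected poor attenders to stay in the primary set. This stands as evidence of intent. A reader who infers that the plan directs the removal of poor attenders goes beyond the text. The discretion clause allows it and no more.

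A reader might also take a low Day 29 VO2peak as an abnormal test result that justifies withdrawal. The documents do not support that. Section 10.1.2 speaks of arrhythmias and other cardiac findings judged for clinical significance, and the Day 29 CPET is done in both arms.

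Nor can one say that withdrawals would fall mostly in one arm. The clause is arm-neutral, Arm A has its own activity instruction, and both arms can deviate on drug, visits or concomitant medication. Only the attendance route is specific to Arm B.

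Two safeguards exist. Section 12.3 displays discontinuations and losses to follow-up by arm with reasons, and 12.5 plans LOCF. They would make some selection visible; neither corrects the primary result.

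Finally, 9.11.1 mixes terms: the PSA item speaks of coming off study treatment, while the opening sentence speaks of the study. Part of the problem may be loose drafting, which is a reason to clarify it.

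**Conclusion.** The gap is real but limited. The plan permits an unblinded, discretionary, non-safety withdrawal that costs a man his week 17 CPET and his place in the primary analysis. It does not prescribe such withdrawals, and nothing in the documents shows that any occurred.

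The size is illustrative: a shift of about 0.1 to 0.5 mL/kg/min in favour of exercise, resting on an assumed 2 or 3 removals out of 20 and an assumed change of 0 to -2.0 in those men. The inflation of the one-sided error also depends on an assumed attendance-outcome correlation. With no such withdrawals, or if attendance is unrelated to outcome, there is no bias. With 20 men per arm, however, a few discretionary decisions can matter. The point justifies a wording change because the remedy is cheap, not because the result is known to be biased.

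**What to change.** - In 9.11.1 and 9.11.2, state that a PI decision ends the study intervention concerned and not follow-up.
- State that every randomised man, whatever his attendance, is invited to the scheduled Day 113 CPET and functional tests and is analysed in his assigned arm, unless he withdraws consent or testing is judged unsafe for him. With that CPET he meets the 12.1 definition of the primary set.
- Leave the criteria for stopping treatment as they are.
- Reconcile 6.1.4 with 9.11.3. The first replaces, and leaves out of the sample size, men who do not receive their assigned treatment. The second replaces only men who withdraw before the baseline primary assessment, which under 9.4 precedes randomisation. Unreconciled, 6.1.4 could still remove the same men.
- Bring 6.4 into line with 12.1 in the same amendment.

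Deleting protocol deviation and administrative issues from the list would not be enough, because the list is open-ended and the general discretion would remain. No new attendance record is needed; 12.3 already covers it.

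The cost is protocol wording and an already scheduled visit for a few men. Keeping poor attenders may make the estimated effect slightly smaller. Men who withdraw consent or cannot safely be tested will still be missing, so the change reduces the selection without removing every loss.
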